## Scientific Background

Laryngomalacia (LM) is the most common cause of stridor in infants. Symptoms of gastroesophageal reflux (GER) are often seen in the setting of LM; therefore, acid suppression therapy (AST) has been empirically used in the management of this disorder. Our team recently performed a retrospective chart review assessing improvement of airway and dysphagia symptoms, weight gain, and need for surgery with AST. We have found that there was a similar improvement between LM severity groups and the majority of patients received AST. It is unclear if these improvements are due to AST or natural resolution of the disease. With heightened concerns of side effects related to AST in infants, particularly among those born prematurely, judicious use of these medications is needed. We are now performing a prospective study looking at the outcome differences in patients with laryngomalacia who are evaluated by speech language therapy (SLP) alone versus those with SLP evaluation and AST. There is no gold standard in treating mild and moderate LM patients and therefore this study would help establish these guidelines.

## Study Objectives

Purpose: To determine the outcome differences in patients 6 months and younger with laryngomalacia and dysphagia who are evaluated by speech language therapy (SLP) alone versus those with both SLP evaluation and acid suppression therapy (AST)

Hypothesis: We hypothesize that there will be no differences in outcomes between those that had SLP alone versus those that had both SLP and AST.

## Study Design & Methods

Design: Prospective clinical trial with survey

### Methods:

All Department of Pediatric Otolaryngology Airway clinic patients with a referral diagnosis of laryngomalacia will have their medical records screened for eligibility. All eligible families with infants that qualify for the study will be approached the day of clinic by their licensed physician to discuss the study. They will be given the Pittsburgh Airway Symptom Score (PASS) questionnaire and the Infant Gastroesophageal Reflux Questionnaire (I-GERQ-R) at the beginning of the appointment. The physician will then perform the standard procedures at the clinic appointment. The Flexible Laryngoscopy Findings sheet will be filled out in conjunction with the clinic procedures for objective data. The surveys will then be scored to determine true GERD (score  $\geq 16$ ) and severe laryngomalacia (LM) (RED questions on the PASS), which would further exclude these patients. There are 12 total questions on the I-GERQ-R. On the PASS, questions 1 & 2 are in the GREEN category and signifies mild LM, YELLOW signifies moderate LM, and RED is severe LM. On the PASS questionnaire, "Yes" to either #1 or #2 and

nothing else is mild LM, "yes" to at least one #3-5 and none of #6-10 is moderate LM, and "yes" to any of the #6-10" indicates severe LM. There are 10 total questions on the PASS.

Mild and moderate LM patients will be block randomized the day before the appointment to receive speech language therapy alone or speech language therapy with famotidine (Pepcid). Both treatments are standard of care in these patients as well as watchful observation. Speech language therapy is part of the normal clinic visit for LM patients. There is no gold standard of care for LM, therefore this trial is important to establish this. Patients will be randomized in both mild and moderate LM blocks before the appointment, as providers are unaware of the severity until the time of the appointment. After the appointment, if the family does not want to participate, the name will be taken off the randomization sheet completely or off the unused block.

These patients will then be re-evaluated at their follow up appointment in 1 to 4 months. The families will take the PASS and I-GERQ-R surveys again to determine LM severity. If Pepcid is discontinued due to intolerance of side effects, they will be kept in the study in the same arm. If the family opts out of the follow-up appointment or they do not need to follow-up in-person, families will take the post surveys via REDCap or by mail. A REDCap link will be sent along with a letter to the caregivers to the caregivers' email address on file. If the families do not fill out the surveys within 2 weeks, paper copies of the surveys along with a letter to the caregivers will be sent to the caregivers' home address on file. If the families do not return the paper copy or the electronic copy of the surveys, researchers will call the participants for a reminder and will ask if the family wants another paper copy or survey link. The family may also answer the survey questions over the phone.

## **Eligibility Criteria**

### **Inclusion:**

- Pediatric patients ages 0 to 6 months who do need meet the criteria at the initial appointment for supraglottoplasty
- Seen in UPMC CHP Otolaryngology Department
- Laryngomalacia without prolonged (>20 seconds) cyanosis, apnea, nor failure to thrive.

### **Exclusion:**

- Children over the age of 6 months old will be excluded from participation.
- Premature infants (<37 weeks gestation)
- Patients with lung disease.
- Laryngomalacia with cyanosis, apnea, and failure to thrive
- Sleep induced laryngomalacia
- Patients with craniofacial abnormalities
- Patients with a syndrome
- Patients with additional airway abnormalities, seen before or at consult
- Patients with symptoms that necessitate surgery
- Patients with prior cardiac surgery
- Patients with AST prescribed prior to the initial ENT consult.

# Study Objectives

Aim: To determine the outcome differences in patients 6 months and younger with laryngomalacia and dysphagia who are evaluated by speech language therapy (SLP) alone versus those with both SLP evaluation and acid suppression therapy (AST)

# Study Outcomes

## Primary Outcome

- Airway Symptom Score Change From Consult (Baseline) to 3 Month Follow-up Appointment.
  - This will be parent-reported and measured using the Pittsburgh Airway Symptom Score (PASS) questionnaire. The PASS is a scale from 0-10 with a higher score indicating a worse outcome. This outcome will be assessed at the consult and the 3 month follow-up appointment.
- Infant Gastroesophageal Reflux Questionnaire (I-GERQ-R) Score Change From Consult (Baseline) to 3 Month Follow-up Appointment.
  - This will be parent-reported. There are 12 questions on the surveys on a scale of 0-42. A higher score indicates a worse outcome. Those with a score of  $\geq 16$  on this survey at the initial consult are excluded from the study, indicating true gastroesophageal reflux disease (GERD). This outcome will be assessed at the consult and the 3 month follow-up appointment.
- Change in Incidence of Airway Symptoms From Consult up to 1 Year Assessed Via Electronic Medical Chart Review.
  - Change in incidence of airway symptoms from consult up to 1 year assessed via electronic medical chart review. Notes from the Department of Otolaryngology will be reviewed which include reported symptoms from caregivers and symptoms seen upon exam. Airway symptoms included periods of apnea, chest wall retractions, cyanosis, stridor, noisy breathing, and increased respiratory rate.
- Change in Incidence of Dysphagia Symptoms From Consult up to 1 Year Assessed Via Electronic Medical Chart.
  - Change in incidence of dysphagia symptoms from consult up to 1 year assessed via electronic medical chart review. Notes from the Department of Otolaryngology will be reviewed which include reported symptoms from caregivers and symptoms seen upon exam. Dysphagia symptoms included choking, coughing, gagging with feeds and/or emesis after feeds.

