## Sample Size Calculation

Based on data from Dang et al [1], 62 participants per group will be needed to address the hypothesis that there is no difference in airway symptom improvement between AST and no-AST groups with alpha=.05 and power=.80 (two-tailed Fisher's exact test, G\*Power 3.1). Target enrollment will be 160 participants (80 in the AST group and 80 in the no-AST group, with 40 with mild laryngomalacia and 40 with moderate laryngomalacia in each group) to account for attrition.

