## **Analyses**

Stata/SE 16.1 will be used for all statistical analysis.  
P value < .05 will be used for statistical significance.

Baseline characteristics will be compared between AST and no-AST groups using Chi-squared or Fisher's exact test for categorical data and t-test (normally distributed) or Wilcoxon rank-sum (not normally distributed) for continuous data. Primary outcome measures will be change in LASS and I-GERQ-R scores from initial visit to follow-up and change in airway and dysphagia symptoms assessed by chart review during the 1 year following the initial visit. The LASS and I-GERQ-R scores will be compared between initial and follow-up surveys using Wilcoxon signed-rank tests. Change scores (post-pre) will be calculated for LASS and I-GERQ-R, and differences in the improvement in scores based on laryngomalacia severity or randomization group will be evaluated using Wilcoxon rank-sum tests. Associations between LASS or I-GERQ-R and time between initial and follow-up surveys will be evaluated using Spearman rank correlation. Symptoms and weight at initial and follow-up visits will be compared using McNemar's and Wilcoxon signed-rank tests, respectively. Change in weight percentile based on laryngomalacia severity or randomization group will be evaluated using Wilcoxon rank-sum tests.

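### The 1-year chart-review airway primary has no stated coding unit and only a within-infant McNemar test, so it does not yield the between-arm airway symptom improvement on which the trial was sized

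*Combined protocol and SAP*

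**What the plan says.** The third primary outcome is "Change in Incidence of Airway Symptoms From Consult up to 1 Year Assessed Via Electronic Medical Chart Review". It is taken from otolaryngology notes, covering both caregiver reports and examination, and its content is "Airway symptoms included periods of apnea, chest wall retractions, cyanosis, stridor, noisy breathing, and increased respiratory rate". No rule turns the six items into a result for one infant.

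The only analysis for it is in Analyses: "Symptoms and weight at initial and follow-up visits will be compared using McNemar's and Wilcoxon signed-rank tests, respectively". That section names rank-sum tests by randomisation group for the questionnaire change scores and for weight percentile, but no between-arm test for chart-review symptoms.

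The Sample Size Calculation takes 62 per group from a two-tailed Fisher's exact test of "no difference in airway symptom improvement between AST and no-AST groups". It neither defines improvement nor gives the assumed rates.

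Three other places bear on where infants start:
- Scientific Background: "Laryngomalacia (LM) is the most common cause of stridor in infants".
- Methods: recruitment is from laryngomalacia referrals ("All Department of Pediatric Otolaryngology Airway clinic patients with a referral diagnosis of laryngomalacia will have their medical records screened for eligibility"). Only mild and moderate cases are randomised. Mild needs a yes to item 1 or 2 of the airway questionnaire (PASS), and moderate needs "at least one #3-5 and none of #6-10 is moderate LM".
- Exclusion: "Laryngomalacia with cyanosis, apnea, and failure to thrive". The inclusion list words this restriction differently, qualifying cyanosis by duration.

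**The concern.** McNemar's test needs a yes/no status at each visit and asks whether status changed between visits. The trial's question is whether change differed between arms. A Fisher test of improvement needs one improved/not-improved result per infant, and neither Primary Outcome nor Analyses creates one.

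The missing coding rule matters because the two obvious readings behave very differently. Under any symptom, an infant who loses retractions but keeps stridor is unchanged, and so is one who gains apnea on top of stridor. Such an outcome could lose sensitivity to a difference in a trial whose hypothesis is that there is none. Under separate symptoms, those changes are visible but spread over six tests. If the choice stays open, it can be made after the data have been seen.

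**Working it through.** **1. The plan's own figure.** No improvement rates are given, so 62 per group cannot be reproduced forward. Solving exact two-sided Fisher power for 80% at 62 per group gives pairs such as 50% vs 24.5%, 70% vs 44.3%, 80% vs 55.3%, 90% vs 68.6% and 95% vs 76.8%. These are differences of about 0.18 to 0.26. So 62 is plausible for a binary improved/not-improved result compared between arms. The target of 80 per group matches 22.5% attrition: 62 / (1 − 0.225) = 80.

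**2. Sized variable against analysed variable.**

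| | Sample Size Calculation | Analyses |
|---|---|---|
| Unit | improvement per infant (undefined) | symptom status per visit |
| Contrast | AST vs no AST | initial vs follow-up visit |
| Test | Fisher's exact | McNemar's |

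The right-hand column does not produce the left-hand one.

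**3. Any-symptom coding: room to worsen.** Infants able to go from absent to present = 160 × (1 − baseline prevalence). The prevalence is not in the documents; assumed range 0.80 to 1.00.

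| Assumed prevalence at consult | 0.80 | 0.90 | 0.95 | 0.98 | 1.00 |
|---|---|---|---|---|---|
| Can register worsening, of 160 | 32 | 16 | 8 | 3 | 0 |

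With an empty worsening cell, exact McNemar P = 2 × 0.5^b for b cleared infants. b = 5 gives 0.0625 and b = 6 gives 0.031. Six infants are 6/124 = 4.8% of the 124 that the calculation requires. This is a pooled before/after result and says nothing about the arms.

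**4. Illustration of sensitivity (all rates assumed).** 62 per arm. Noise (stridor or noisy breathing, counted once) is present in 100% at consult and persists in 80% of both arms. Retractions (50% at consult) and fast breathing (30%) persist in 70% of arm A and 35% of arm B. New onset is 5%.
- Retractions at follow-up: A 0.5 × 0.70 + 0.5 × 0.05 = 0.375; B 0.5 × 0.35 + 0.5 × 0.05 = 0.200.
- Fast breathing: A 0.3 × 0.70 + 0.7 × 0.05 = 0.245; B 0.3 × 0.35 + 0.7 × 0.05 = 0.140.
- Any symptom: A 1 − 0.2 × 0.625 × 0.755 = 0.906; B 1 − 0.2 × 0.800 × 0.860 = 0.862.
- Fewer symptoms than at consult, summing over all combinations of change: A 0.365; B 0.544.

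| Between-arm comparison | Power |
|---|---|
| Any symptom (Fisher) | 7% |
| Retractions alone (Fisher) | 51% |
| Improved yes/no (Fisher) | 47% |
| Improved/unchanged/worse (rank test) | about 48% |

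With noise persisting in 90% of both arms, any symptom has 3% and the three-level result about 58%.

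**5. Other assumed rates.** Four further scenarios used consult prevalences of 2% apnea, 30% retractions, 2% cyanosis, 90% stridor, 90% noisy breathing and 20% fast breathing, with resolution differing between arms for every symptom. About 99.5% of infants then have some symptom at consult. Any-symptom coding leaves 39–51% of infants who improved but kept a symptom recorded as unchanged. Power, any symptom vs symptom count, was 0.50 vs 0.78, 0.36 vs 0.50, 0.39 vs 0.81 and 0.68 vs 0.58. The any-symptom form is weaker in three of the four.

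**The case against.** A reader might infer that partial improvement and worsening cannot register at all. The documents do not support that. They never state any-symptom coding, and separate McNemar tests per symptom are at least as natural a reading. On that reading, retractions and fast breathing can move either way. Apnea and cyanosis, restricted at entry, can newly appear. In the illustration, a between-arm test on retractions alone (51%) does as well as the three-level result. That objection stands, and so binary coding is not in itself the flaw.

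It is also fair that the illustration is favourable to the concern. It holds noise persistence equal in both arms and puts the whole effect on the other two signs. The between-arm test on any symptom is not one the plan names.

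Graded airway change is partly covered by another primary, the 0–10 PASS change, which is compared by arm. A worse course could also show in supraglottoplasty, need for AST and adverse events. But the PASS outcome is parent-reported at about 3 months, so it does not replace a chart outcome running to 1 year.

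Finally, a two-tailed Fisher test implies that the authors had an improved/not-improved variable in mind. Probably so, but neither Primary Outcome nor Analyses defines it. The separate-symptom reading does not supply it either: it gives six tests inside one of four primaries at P < .05, with no multiplicity rule and with two overlapping items (stridor and noisy breathing).

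**Conclusion.** The point holds in a limited form. What rests on the text alone is that the coding unit is unstated, the only named test compares visits, and the per-infant, between-arm improvement used for sizing is never produced.

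The ceiling is conditional on any-symptom coding and on near-universal symptoms at consult. The latter is a strong inference from the referral population and the severity definitions, but no prevalence is given and the PASS item texts are not in the documents. Under those two conditions, between 0 and 8 of 160 infants could register worsening at 95–100% prevalence, and improvement counts only when every symptom has gone. The power figures illustrate assumed rates and do not estimate this trial's power.

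This should be corrected before analysis. It does not show that the outcome is blind or that the trial cannot answer its question.

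**What to change.** In Primary Outcome and Analyses:
1. Abstract each listed symptom as present or absent at consult and at one named follow-up note, counting stridor and noisy breathing once.
2. Classify each infant as improved, unchanged or worse (fewer, the same or more symptoms), and state in advance how new apnea or cyanosis is classified.
3. Compare the randomised arms on this three-level result. Use improved yes/no with Fisher's exact test as the binary in the Sample Size Calculation, and state there its definition and assumed rates.
4. Keep McNemar's test as a description of change over time. Report individual symptoms by arm, including new apnea and cyanosis, as supportive results.

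Separately, the inclusion and exclusion wordings on cyanosis and apnea must be reconciled, because they determine which symptoms can be present at consult.

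The cost is SAP wording and one line on the abstraction form; the same notes are already read. The downside is that a count weights symptoms equally, which the supportive by-symptom table partly offsets.

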## Secondary Outcomes

- Weight (kg) From Consult up to 1 Year.
  - Weight change in kilograms assessed from medical chart review from consult up to 1 year
- Number of Participants With the Need for Supraglottoplasty Surgery (Escalation of Treatment) up to 1 Year.
  - The need for escalation of treatment with supraglottoplasty surgery will be assessed through medical chart review up to 1 year.

- Number of Participants With the Need for Acid Suppression Therapy Medication (Famotidine) From Speech Language Therapy Alone Group From the Day After the Consult up to the 3 Month Follow up Appointment.
  - The speech language therapy alone group will be assessed for the need for a prescription for acid suppression therapy (famotidine) from the day after the consult up to 1 year.
- Number of Participants With Each Type of Laryngomalacia (Types 1-3) Found on the Flexible Laryngoscopy Procedure at the Consult.
  - All patients will be scoped with a flexible laryngoscopy at the initial consult and the type of laryngomalacia (Types 1-3) will be noted.
- Number of Participants With the Need for a Different Acid Suppression Therapy Medication (Other Than Famotidine) From the Day After the Consult up to the 3 Month Follow up Appointment.
  - Both groups will be assessed for the need for a different acid suppression therapy medication (other than famotidine) from the day after the consult up to the 3 month follow up appointment.

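### The two chart-review primaries have no assessment time within the year and no between-arm test, so as planned they cannot separate acid suppression from natural resolution

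*Combined protocol and SAP*

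**What the plan says.** The Primary Outcome section lists four primaries. The two questionnaire scores are tied to the consult and the 3-month follow-up appointment. The two chart outcomes are not: "Change in Incidence of Airway Symptoms From Consult up to 1 Year Assessed Via Electronic Medical Chart Review" and, for dysphagia, "Change in incidence of dysphagia symptoms from consult up to 1 year assessed via electronic medical chart review". Their source is routine clinic documentation: "Notes from the Department of Otolaryngology will be reviewed which include reported symptoms from caregivers and symptoms seen upon exam".

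The Analyses section repeats the one-year span, "change in airway and dysphagia symptoms assessed by chart review during the 1 year following the initial visit". It then tests symptoms at initial and follow-up visits with McNemar's test, without saying which follow-up visit is meant. Between-arm rank-sum tests are listed for the questionnaire change scores and for weight percentile, but none is listed for chart symptoms. A check on elapsed time (Spearman correlation) is listed for the questionnaires only.

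On visits, the Methods say: "These patients will then be re-evaluated at their follow up appointment in 1 to 4 months". An in-person visit is not guaranteed, and mailed surveys are also allowed: "If the family opts out of the follow-up appointment or they do not need to follow-up in-person, families will take the post surveys via REDCap".

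The Scientific Background gives the reason for the trial. Of the improvement seen in the team's earlier chart review, it says: "It is unclear if these improvements are due to AST or natural resolution of the disease".

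In Secondary Outcomes, the record of other AST drugs stops at the 3-month visit: "Both groups will be assessed for the need for a different acid suppression therapy medication (other than famotidine) from the day after the consult up" (the sentence ends by naming that visit). The item on famotidine in the speech-language-therapy-alone arm has a 3-month heading and a 1-year description.

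**The concern.** If symptoms may go away untreated, time since consult is a main determinant of whether a note records them. A note at 2 months and a note at 11 months are not the same measurement, yet nothing in the plan distinguishes them.

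The listed test adds a second problem. A within-infant before-and-after comparison will show improvement whether the cause is the drug or the infant's growth. It would do so in both arms, and it does not compare them. The Sample Size Calculation, by contrast, assumes a Fisher test between arms on airway symptom improvement, with no time point given.

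At stake is whether two of the four primaries can answer the trial's question. Two analysts with the same charts could choose different notes and report different results, both consistent with the plan.

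**Working it through.** **Step 1. Is the time point fixed anywhere?** There are three possible readings.
- *The follow-up visit is the 1-to-4-month appointment.* This conflicts with the one-year span in both Primary Outcome and Analyses. It also yields no note for a family that answers remotely instead of attending.
- *Any one note in the year supplies the follow-up value.* Follow-up times are then mixed, with no selection rule.
- *All notes in the year are pooled.* Infants seen more often, or for longer, have more chances to have a symptom recorded.

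No reading gives a defined outcome.

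**Step 2. The plan's own figure.** The plan states 62 per group (Fisher, two-tailed, alpha .05, power .80) and 80 enrolled. The improvement rates behind it are not given, so 62 can be neither confirmed nor refuted. Back-solving with exact Fisher power at 62 per group, it fits pairs such as 40% vs 65.8%, 50% vs 75.5% or 60% vs 83.7%. Enrolment is consistent with 22.5% attrition: 62 / (1 − 0.225) = 80.

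**Step 3. How much does timing matter?** The documents give no resolution time, so the inputs here are assumptions: constant-rate resolution, a median of m = 2 to 8 months without AST, a rate doubled by AST, and 62 per arm. The proportion still symptomatic at month t is

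S0(t) = 0.5^(t/m) without AST, and S1(t) = S0(t)² with AST.

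For m = 3: at month 3, 0.50 − 0.25 = 25.0 points; at month 12, 0.0625 − 0.0039 = 5.9 points. Power is exact, for the two-sided Fisher test.

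| Median (months) | Difference, month 3 | Power | Difference, month 12 | Power | Power, notes spread evenly over months 1–12 | Power, notes spread evenly over months 1–4 |
|---|---|---|---|---|---|---|
| 2 | 22.9 | 81% | 1.5 | about 0% | 40% | 73% |
| 3 | 25.0 | 78% | 5.9 | 16% | 54% | 70% |
| 4 | 24.1 | 74% | 10.9 | 55% | 61% | 64% |
| 6 | 20.7 | 60% | 18.8 | 78% | 64% | 50% |
| 8 | 17.6 | 49% | 22.9 | 81% | 64% | 41% |

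Late assessment loses power for medians of 2 to 4 months and gains it for 6 to 8. A 1-to-4-month window beats the full-year spread for medians of 2 to 4 months (only narrowly at 4) and is worse for 6 and 8.

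**Step 4. What if note times differed by arm, with no drug effect?** The spurious difference is S0(t₁) − S0(t₂). Month 3 against month 4 gives 6 to 10 points over the same medians, and Fisher rejects in 9% to 19% of trials. Month 3 against month 6 gives 18 to 25 points and rejection in 49% to 81%. Equal timing gives 3% to 4%. These figures show sensitivity only. The documents do not say that timing will differ by arm.

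**The case against.** The strongest reply is that a one-year horizon is a legitimate choice beside two questionnaire primaries fixed at 3 months, so an early effect is not left unmeasured. Randomisation should also balance note timing on average. Both points stand. They answer a complaint about the length of the window, but they supply neither the missing note rule nor the missing between-arm test.

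A reader might infer three stronger things that the documents do not support.
- *That late notes will hide an AST effect.* This holds in the model only for the faster assumed medians and reverses for the slower ones. The near-zero power at month 12 also requires every note to be written then; an even spread over months 1 to 12 gives 40% to 64%.
- *That one arm will be seen later and so look better.* Follow-up depends on clinical need and no masking is described, so this is possible, but nothing in the documents shows it.
- *That after 3 months treatment exposure is undocumented.* The famotidine item describes tracking in the speech-language-therapy-alone arm to 1 year, although its heading says 3 months. The clear gap is other AST drugs.

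Nor would simply moving the chart primaries to a note at 1 to 4 months settle the matter. Timing still matters inside that window: with no drug effect, month 1 against month 4 differs by 21 to 46 points under the same model. Infants followed only by remote survey might have no note in the window. They may be the improved ones, and the plan does not impute missing data.

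**Conclusion.** The concern holds in a limited form. Both chart primaries lack an assessment time and a note-selection rule, and the only test listed for them is within-patient. As written they mix follow-up times, do not compare the arms, and cannot separate AST from natural resolution. This conclusion rests on the text alone.

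The size and direction of any power loss are not established. From month 3 to month 12 the change in power runs from a loss of about 81 points (median 2 months) to a gain of about 32 points (median 8 months). That range rests on an assumed constant rate, an assumed doubling under AST, 62 per arm, and a Fisher comparison that the Analyses section does not list for these outcomes. It shows that timing matters; it does not show that a 1-year window is wrong.

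**What to change.** In Primary Outcome and Analyses:
- Record the date of each Otolaryngology note used.
- Compare the chart outcomes between randomised arms with an analysis that accounts for time since consult. Options are time to first symptom-free note, treated as interval-censored between the last symptomatic and first symptom-free notes, or symptom status by arm adjusted for note time.
- State in advance which note counts for any single-time comparison, and what is done with several notes or none.
- Report a contrast in a window around 3 months as supportive. It need not become the primary.
- Report the distribution of note times by arm.

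In Secondary Outcomes, extend the count of other AST drugs to 1 year, and reconcile the famotidine item's 3-month heading with its 1-year description.

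The cost is wording, a date field and somewhat more analysis work, since the same charts are already reviewed for the year. One limit remains: note timing is still driven by clinic attendance, and interval-censoring or adjustment reduces that dependence without removing it. This is why the note times need to be shown by arm.
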